## **TRIAL DESIGN**

The study is designed as a multi-center, randomized, controlled, researcher and volunteer blinded, with two parallel groups (intervention and placebo). In addition, the randomization will be performed as block randomization with a 1:1 allocation.

## **MATERIAL AND METHODS**

### **Registration and adherence to SPIRIT standards**

This study will follow SPIRIT (Standard Protocol Items: Recommendations for Interventional Trials) guidelines for randomized clinical trials, and results will be reported following 2010 CONSORT (Consolidated Standards of Reporting Trials) standards (<http://www.consort-statement.org/>). In addition, it is important to mention that we intend to register the study on ClinicalTrials.gov as soon as this proposal of study is approved and also perform the sequential dating of each protocol version in order to mitigate potential confusion over which document is the most recent.

## Population and design of the study

In order to perform this research project, it is proposed to recruit and select 70-80 amateur triathletes, between 25 to 45 years, both sexes, residing in the city of São Paulo, Brazil, who will be participating in the same triathlon competition.

Regarding the sample size, it was determined using G\*Power software (version 3.1.9.6). The analysis was conducted using the F tests - ANOVA: repeated measures, within-between interaction option to accommodate the mixed design of the study, which includes two groups and five repeated measurements. It is important to mention that to carry out the sample size calculation alignment with the study's primary objective, which is associated with the salivary IgA, we used the data presented in the study performed by [name] et al., 2019. In agreement with this data, the following parameters were used to calculate the required sample size: Effect size (f): 0.15 ([name] et al., 2019). Alpha error probability ( $\alpha$ ): 0.05. Power (1- $\beta$  error probability): 0.85. Correlation among repeated measures: 0.5. Nonsphericity correction ( $\varepsilon$ ): 1. Based on these inputs, the total sample size required to achieve the desired power of 0.85 is 62 participants. Thus, 70-80 athletes will be included in this study. This sample size will be distributed equally between the two groups (35-40 participants per group).

It is noteworthy to clarify that we intend to separate the volunteers into two groups: male amateur triathletes, which will be composed of 40-45 individuals, and female amateur triathletes, which will be composed of 30-35 individuals. This discrepant number is associated with the fact that the number of male participants in the triathlon competition is higher than the number of female participants. For instance, in 2022, the triathlon competition "IronMan 70.3 São Paulo" presented a total number of 1858 participants, of which 1237 completed the competition. In fact, whereas 1027 men completed the competition, only 210 women conclude this same competition (available in <https://www.ironman.com/im703-sao-pauloresults>). Based on these pieces of information, we decide to not separate equally the number of volunteers to compose the groups of male and female individuals. In order to achieve the number of volunteers' groups (male and female) we will invite the athletes subscribed to the triathlon competition through direct contact with the athletes' consultancies, and also by sending the invitation to their social media.

All individuals will be initially evaluated through clinical examinations, and it will exclude the volunteers who: (1) report intolerance to lactose; (2) are under any type of pharmacological treatment; (3) report chronic rhinopathy; (4) have autoimmune diseases; (5) report the occurrence of non-airway recurrent infections. Besides, (6) whether any data from a volunteer is missing, this participant will be excluded from the study. As an inclusion criterion, it will inquire if the participants already presented the occurrence of any upper airway symptoms after an official triathlon competition. In this sense, according to Andersen et al. (2013), the incidence of diseases in triathletes is similar to other individual sports, such as marathons and swimming, with an incidence of approximately 30% being reported. It is worth clarifying that, according to the same authors, any health problems that are not related to the musculoskeletal system are considered a disease in this context, particularly in terms of the occurrence of similar symptoms of flu post-competition.

It is also important to cite that the participants will be instructed not to consume products containing probiotics or other fermented drinks during the study, and if any volunteer reports the regular habit of consuming such products, he will be oriented to interrupt this consumption for, at least, two weeks before the start of the study (a washout period).

In addition, volunteers invited to perform in this study will receive all the information related to the present study and those to agree in participate will be oriented to sign the Informed Consent Term, which must be previously approved by the Research Ethics Committee of the Federal University of São Paulo (UNIFESP), Brazil. The study is in agreement with both the Ethical Standards and the Declaration of Helsinki.

It is important to clarify that there will be no official data monitoring committee established for this study. Thus, the only institution responsible for following the development of the study is the Ethics Committee, through regular reports.

In order to improve the volunteers' adherence to the present study we will offer and provide the results concerning the performance of each one in the physical tests, especially concerning the cardiopulmonary test, as well as those related to the laboratory tests. All physical and laboratory tests are following described.

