### **Statistical analysis**

All data obtained during the development of this study will be added to a unique file, preferentially in an Excel file, which will be available to all researchers not only to consult and check the data quality/accuracy but also to add any results through GOOGLE-DRIVE. It is noteworthy to clarify that, to perform all the statistical analysis proposed here, we will follow the "intention-to-treat" (ITT) analysis, not only because it is recommended as an analysis strategy for randomized studies but also to be possible to maintain the sample size, as well as to use the data obtained from the participants regardless of whether they complete the study since ITT considers all randomized participants in the analysis, whether they drop out or not. In addition, the multiple imputation (MI) method will be applied to handle missing data since

MI fills in missing values by generating plausible numbers derived from distributions of and relationships among observed variables in the data set. Beyond these analyses, in order to check and increase the reliability of the results obtained in the ITT analysis, we also intend to conduct the statistical analysis regarding the per-protocol (PP) analysis, which will be used exclusively the complete data obtained from the volunteers.

After all data will be added to the Excel file and the data quality/accuracy is checked by the researchers, these data will be initially compared with the Gaussian curve, and normality determined for each variable.

If the variable presents a parametric behavior, the mean and standard deviation will be used, and they will be compared by using the ANOVA test for repeated measures with post hoc tests for intragroup (longitudinal) and intergroup (cross-sectional) analysis.

On the other hand, if the data present a non-parametric behavior, they will be represented by median and interquartile ranges, and they will be compared by using Friedman's test with Müller-Dun post hoc test for intragroup (longitudinal) and the Kruskal-Wallis test with Müller Dunn's post hoc test for intergroup (cross-sectional).

Using Pearson (for parametric values) or Spearman tests (for non-parametric values), the correlation between the variables studied will be evaluated.

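### The sample size of 62 assumes perfect sphericity without a stated reason, and the planned repeated-measures ANOVA names no correction should sphericity fail

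*Combined protocol and SAP*

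**What the plan says.** The sample size paragraph (Population and design of the study) uses G*Power with the option "ANOVA: repeated measures, within-between interaction option to accommodate the mixed design of the study", "which includes two groups and five repeated measurements". The inputs are "Effect size (f): 0.15", alpha 0.05, power 0.85, and "Correlation among repeated measures: 0.5. Nonsphericity correction", the last set to 1. The stated result is that "the total sample size required to achieve the desired power of 0.85 is 62 participants". The plan then enrols 70-80 athletes, 35-40 per group. It gives no reason for epsilon = 1 and no dropout rate.

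The Sample collection section sets the five occasions: before intake starts (30 days before the race), 24 hours before, immediately after, 72 hours after and 14 days after.

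The Statistical analysis section says of normally distributed variables that "they will be compared by using the ANOVA test for repeated measures with post hoc tests", within and between groups. Variables that are not normal go to Friedman and Kruskal-Wallis tests. No sphericity test, Greenhouse-Geisser or Huynh-Feldt correction, or mixed model is mentioned, and the group-by-occasion interaction is not named as the primary test.

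**The concern.** Epsilon = 1 means that the difference between any two occasions has the same variance. Here the gaps between occasions run from about one day to 44 days, and one sample is taken straight after the race. If neighbouring samples agree more closely than distant ones, or if spread changes after the race, that condition fails. The protocol's own rationale is that strenuous competition disturbs immune measures, so the assumption deserves a reason.

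The sample size and the analysis lean on the same assumption, and this is the only power figure in the plan. If sphericity fails and nothing is corrected, the F test rejects a true null more than 5% of the time. If a correction is applied, the test has less power than the calculation promised. With no rule fixed in advance, the choice could be made after the data are seen, and it changes the p-value.

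**Working it through.** **Inputs from the sample size paragraph.** f = 0.15, alpha = 0.05, k = 2 groups, m = 5 occasions, rho = 0.5, epsilon = 1, target power 0.85.

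**Formula (G*Power default, noncentral F).**
- lambda = f² × N × m × epsilon / (1 − rho)
- df1 = (k − 1)(m − 1) × epsilon
- df2 = (N − k)(m − 1) × epsilon

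**Step 1: reproduce the stated figure.** At N = 62, lambda = 0.0225 × 62 × 5 / 0.5 = 13.95, df1 = 4, df2 = 240, and power is 0.857. N = 60 gives 0.844. So 62 is the smallest equal-arm total that reaches 0.85, and the plan's figure is confirmed.

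**Step 2: corrected test, other inputs unchanged.** The documents give no epsilon, so the values below are assumptions. For example, at epsilon 0.7 and N = 62, lambda = 13.95 × 0.7 = 9.765, df1 = 2.8, df2 = 168, and power is 0.750.

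| Epsilon (assumed) | Power, N = 62 | Power, N = 70 | Power, N = 80 | N for 0.85 |
|---|---|---|---|---|
| 1 | 0.857 | 0.902 | 0.940 | 62 |
| 0.8 | 0.792 | 0.844 | 0.894 | 72 |
| 0.7 | 0.750 | 0.806 | 0.860 | 78 |
| 0.6 | 0.700 | 0.758 | 0.817 | 88 |

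Power of 0.85 is lost below epsilon of about 0.97 at N = 62, 0.82 at N = 70 and 0.67 at N = 80. All of this assumes complete data. As an illustration, 10% losses leave 63 of 70 or 72 of 80, and at epsilon 0.7 power is then about 0.76 or 0.82.

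**Step 3: uncorrected test, type I error.** Simulated for the group-by-occasion F test with 40,000 null trials and 31 per arm. The covariances are assumptions.

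| Assumed covariance | Epsilon | Uncorrected | Greenhouse-Geisser |
|---|---|---|---|
| Equal correlation 0.5 | 1.00 | 5.0% | 4.5% |
| First-order autoregressive by visit order, r = 0.5 | 0.81 | 6.4% | 4.8% |
| First-order autoregressive by visit order, r = 0.7 | 0.69 | 7.1% | 4.8% |
| Post-race SD doubled (SD 1.2 times at 72 h) | 0.67 | 7.1% | 4.8% |
| Exponential decay, 0.95 per day | 0.59 | 8.1% | 4.7% |
| Exponential decay, 0.98 per day | 0.52 | 8.9% | 5.0% |

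A tripled post-race SD (epsilon 0.42) gives 9.5% uncorrected, which is an extreme case.

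**Step 4: do both harms occur together?** A second simulation (20,000 trials per scenario, N = 62, direction of the group difference drawn at random) gave these powers:

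| Epsilon | Uncorrected | Greenhouse-Geisser |
|---|---|---|
| 0.81 | 0.859 | 0.820 |
| 0.59 | 0.868 | 0.769 |
| 0.42 | 0.872 | 0.692 |

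The uncorrected test loses no power. The loss appears only once the correction is applied, and here it is smaller than the formula suggests (0.769 at epsilon 0.59, against 0.700 by formula at 0.6).

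**The case against.** A reader might infer that the stated power is overstated and that the primary test's false-positive rate exceeds 5%, both as established facts. The documents do not support that, for four reasons.

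- They contain no variances, correlations or epsilon for salivary IgA. Uneven spacing alone does not break sphericity, and no passage says that spread widens after the race. The parameter list is introduced as agreeing with the earlier marathon study, so epsilon may have come from there. It is fair to say only that the text gives no reason.
- The two harms are alternatives for a given test, as Step 4 shows.
- The plan enrols 70-80, not 62, and with complete data that absorbs part of the loss.
- The alpha point concerns only the ANOVA route. The plan is silent on correction, which is not the same as ruling it out, and it never names the interaction test as primary.

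All four stand, and they make the point conditional. They do not remove it. The margin above 62 is also the only cover for losses. The eligibility text excludes anyone with missing data, in conflict with the intention-to-treat analysis and multiple imputation planned later, so the full margin may not be available.

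It is also fair that the formula's power figures look more exact than they are. Real power depends on which occasions carry the group difference and can fall above or below the formula, so the table shows the order of the loss and does not predict it.

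**Conclusion.** The concern holds in conditional form. The 62 is computed correctly, but it rests on an unexplained epsilon of 1 and has almost no slack. The analysis section does not say what happens if that assumption fails. If it fails, the ANOVA route offers either a type I error of roughly 6-9% (epsilon about 0.8 down to 0.5, assumed covariances) or a corrected test with power of about 0.70-0.79 at 62, 0.76-0.84 at 70 and 0.82-0.89 at 80 (epsilon 0.6-0.8, by formula, complete data). Failure of sphericity is plausible from the timing and the race, but it is an assumption. Severity: should fix.

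**What to change.** **Statistical analysis section.** Name the group-by-occasion test for salivary IgA and run it as a mixed model for repeated measures with unstructured covariance. With five occasions that means 5 × 6 / 2 = 15 covariance parameters. At the least, specify the Greenhouse-Geisser corrected F test. Fix this before unblinding.

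**Sample size paragraph.** Report power at 62, 70 and 80 over a range of epsilon, for example 0.6 to 1, labelled as an assumption, and state how many losses the 70-80 is meant to cover.

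**Cost.** The changes are to wording. The power statement becomes somewhat less favourable, and the corrected test has slightly less power than the uncorrected one. No extra athletes are needed if the plan accepts power below 0.85 at the lower epsilon values. Holding 0.85 by formula would take 78 complete at epsilon 0.7, above the lower recruitment limit, and 88 at 0.6, above the upper one.

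### The any-missing-data exclusion contradicts the intention-to-treat plan, and the step from 62 to 70-80 athletes carries no stated attrition rate

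*Combined protocol and SAP*

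**What the plan says.** The sample size paragraph under Population and design of the study uses a repeated-measures ANOVA interaction, "which includes two groups and five repeated measurements", with "Effect size (f): 0.15", correlation 0.5 and sphericity correction 1. It concludes that "the total sample size required to achieve the desired power of 0.85 is 62 participants". The next sentence is "Thus, 70-80 athletes will be included in this study". No dropout, non-start or non-finish rate links the two figures.

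The same section explains the unequal numbers of men and women with results from the 2022 edition of the race, which "presented a total number of 1858 participants, of which 1237 completed the competition". Item 6 of its exclusion list then says that "whether any data from a volunteer is missing, this participant will be excluded from the study". The exclusion list in the ethics opinion carries the same rule as item 7.

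The Statistical analysis section commits all analyses to intention-to-treat, including athletes who drop out, with multiple imputation for missing values. Complete data are reserved for a supporting per-protocol analysis.

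Under Sample collection, three of the five samples are timed from the competition: immediately, 72 hours and 14 days after it. The documents do not say how an athlete who does not start or finish is to be sampled.

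**The concern.** Two instructions cannot both be followed. Under item 6, one lost tube or questionnaire removes an athlete who has already been randomised. Under the Statistical analysis section the same athlete stays in and the gap is imputed. The choice matters in two ways.

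- **Bias.** Whether data are complete is known only after randomisation, and it may depend on illness, tolerance of the product or the course of the race. Removing athletes on that basis gives up the protection that the intention-to-treat commitment is meant to provide.
- **Power.** The primary IgA test is planned around 62 athletes. How far 70-80 covers that number depends on the loss, which the plan does not state. The only completion figure in the documents, from the race the volunteers are invited to enter, is lower than the margin allows for.

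**Working it through.** **Inputs**, all from Population and design of the study: f = 0.15, alpha = 0.05, target power 0.85, correlation rho = 0.5, epsilon = 1, k = 2 groups, m = 5 measurements, planned N = 70-80, race completion 1237 of 1858.

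**Step 1: reproduce the plan's figure.** For the within-between interaction:

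- lambda = f² × N × m × epsilon / (1 − rho)
- df1 = (k − 1)(m − 1) × epsilon
- df2 = (N − k)(m − 1) × epsilon

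At N = 62, lambda = 0.0225 × 62 × 5 / 0.5 = 13.95, df1 = 4 and df2 = 240. The noncentral F distribution gives power 0.857. The smallest N reaching 0.85 is 61 (0.851), or 62 with equal groups. The stated 62 is correct. With no loss, power is 0.90 at 70 and 0.94 at 80.

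**Step 2: loss that the margin absorbs.** 1 − 62/70 = 11.4%, and 1 − 62/80 = 22.5%.

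**Step 3: the quoted race.** 1237/1858 = 0.666, so 33.4% did not complete. 70 × 0.666 = 46.6 and 80 × 0.666 = 53.3, or about 47 and 53 athletes. Keeping 62 complete cases at that loss would need 62/0.666 = 93.1, so 94 randomised.

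**Step 4: complete-case power over a range of assumed loss.** The formula is that of Step 1. Half-athletes are rounded down, and the last row is rounded to the nearest athlete.

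| Assumed loss | Complete of 70 | Power | Complete of 80 | Power |
|---|---|---|---|---|
| 10% | 63 | 0.86 | 72 | 0.91 |
| 15% | 59 | 0.84 | 68 | 0.89 |
| 20% | 56 | 0.81 | 64 | 0.87 |
| 25% | 52 | 0.78 | 60 | 0.84 |
| 33.4% | 47 | 0.73 | 53 | 0.79 |

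(At 46 complete cases, power is 0.72.)

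**Step 5: does imputation restore the power?** Suppose 33.4% of athletes give only samples 1 and 2, and the data are analysed by likelihood, which multiple imputation approximates. With Sigma the compound-symmetric covariance (correlation 0.5), Sigma12 its block for samples 1 and 2, and p = 0.666, the group differences over time have covariance V = (4/N) × [p × Sigma⁻¹ + (1 − p) × Sigma12⁻¹ padded with zeros]⁻¹. The effect is scaled to f = 0.15 with full data, and lambda is recomputed for the interaction contrasts.

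- Effect confined to post-race samples (all three, the first two, or one): power about 0.74-0.76 at N = 70 and 0.80-0.83 at N = 80.
- Effect already present at sample 2 and lasting to sample 5: about 0.86 at N = 70 and 0.91 at N = 80.

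So imputation recovers part of the lost information. How much depends on when the effect appears, which the plan does not specify.

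**The case against.** The strongest case on the other side is that the analysis section governs. It keeps all 70-80 athletes, and complete data enter only the per-protocol analysis. A reader might infer from the race figure that 0.85 power is not delivered and that the analysed set will be a self-selected group of finishers. The documents do not support that, for four reasons.

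- The intention-to-treat text says the opposite about who is analysed.
- The plan attaches 0.85 to 62 participants, and that is right. No stated figure is in error.
- The one-third rate is not the plan's attrition figure. It is quoted to explain the male/female split, covers the whole 2022 field, and may count registrants who never started. The volunteers are aged 25-45, clinically screened and medically followed, and may finish more often.
- Nothing says that a non-finisher cannot be sampled. An athlete who withdraws mid-race can still attend at the scheduled times.

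Item 6 also stands among the entry criteria and could be meant for screening data only.

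All of this limits the conclusion, but it does not resolve the conflict. Item 6 refers to any data and to exclusion from the study, is repeated in the ethics opinion, and has no screening limit. The volunteers' own rate is unknown in either direction. Athletes who never start also count here, because they are invited from those registered and begin the product 30 days before the race. On complete cases, a shortfall at N = 70 needs only a little more than 11% loss.

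**Conclusion.** The contradiction between the exclusion rule and the intention-to-treat plan is certain from the text. If the rule is followed, it is a post-randomisation exclusion that can bias the comparison. The power consequence is conditional. On the plan's own inputs, 0.85 needs about 62 athletes with complete data, which 70-80 provides only while the loss stays below 11.4% to 22.5%. The figure of 0.73-0.79 holds only if complete data are required, the volunteers complete at the 2022 field rate, and every non-finisher loses a sample. None of these three is established, so it marks the unfavourable end of a range and is not the expected power. Under imputation the loss is smaller, but at one third missing it still leaves power below 0.85 if the effect appears only after the race. The point should be settled before randomisation.

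**What to change.** 1. Delete exclusion item 6 for randomised athletes, and submit the same change to the ethics committee as an amendment so that its exclusion list agrees. Intention-to-treat with multiple imputation then governs, and complete cases are used only in the per-protocol analysis.
2. State that samples 3 to 5 are sought from every randomised athlete at equivalent times, whether or not the athlete starts or finishes the race.
3. After the sample size calculation, give an expected rate of missing samples with its justification. State that 0.85 needs about 62 athletes with complete data, show the Step 4 table, and note that imputation recovers only part of what is lost.

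Power should not be restated as a flat 0.73-0.79: change 2 is meant to prevent the loss on which that figure depends.

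The cost is protocol wording, an ethics amendment, the effort of following athletes who do not start or finish, and a less favourable, conditional power statement. No extra athletes are needed.
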